4.2.2 Derivation rules

PK concentrations will be reported in ng/mL by the lab and will be converted to ug/mL for analyses.

4.2.3 Presentation of results

Individual concentration data and actual blood sampling times from dose administration for PK assessments will be listed.

Descriptive statistics per time point on concentration data will be presented in tables.

4.3 PHARMACODYNAMICS

4.3.1 Available data

The following pharmacodynamic parameter will be measured: total IgG serum levels, anti-BP180 antibodies, anti-BP230 antibodies serum levels.

4.3.2 Derivation rules

Samples for anti-BP180 antibodies and anti-BP230 antibodies will be diluted until the result falls within the reportable range of [20-200 RU/mL].

SGS	Statistical Analysis Plan		
ARGX-113-2009	Final and Interim Analysis	Final 4.0 of 04NOV2024	

For anti-BP180 antibodies:

- The value for analysis will be the result with the lowest dilution factor and with value ≤200 RU/mL, multiplied by the dilution factor.
- If the result is <20 RU/mL, the value for analysis will be imputed by 20 RU/mL, multiplied by the dilution factor.
- If at a dilution factor (D1) the result is above 200 RU/mL, and at the
 next higher dilution factor (D2) the result is < 20 RU/mL, the value for
 analysis will be derived as D1 x 200 RU/mL.
- If all the results up to dilution factor 32 are above 200 RU/mL, then the
 value for analysis will be imputed by 6400 RU/mL (32 * 200), even if
 the result at a higher dilution factor gives a value below 6400 RU/mL.
- If the result is above 200 RU/mL in the original non-diluted sample and no higher dilution factors are available, the value for analysis will be imputed by 200 RU/mL.

For anti-BP230 antibodies:

- If in the original (non-diluted) sample the result is above 200 RU/mL, then the value for analysis will be imputed by 200 RU/mL, even if the result at a higher dilution factor is ≤200 RU/mL.
- If the result in the original sample is <20 RU/mL, the value for analysis will be imputed by 20 RU/mL.

Total IgG results expressed as below or above the limit of quantification (BLQ or ALQ, respectively) will not be imputed.

Changes and percent changes vs baseline will be calculated. Participants with a baseline value below the limit of quantification (BLQ) or with a result <20 RU/mL (for anti-BP180 and anti-BP230 antibodies) will be excluded when presenting the actual values, the changes from baseline and the percent changes from baseline. This will be explained by a footnote in the appropriate tables. Limits of quantification are provided by the lab.

In addition, for all pharmacodynamic endpoints, descriptive statistics of the actual vales will also include GM, and GSD. GM and GSD are not applicable for descriptive statistics of the absolute changes from baseline. For these selected endpoints, descriptive statistics of percent changes from baseline will also include GM and GSD. GM and GSD of percent changes from baseline are calculated as $100X\{exp(\theta)-1\}$ where θ is respectively the arithmetic mean and arithmetic SD of a variable calculated as log(aval)-log(base).

4.3.3 Presentation of results

All pharmacodynamic endpoints will be summarized by means of descriptive statistics at each analysis visit. Actual values, changes from baseline and percent changes from baseline will be tabulated.

Tables with descriptive statistics will be presented including all available data and will be repeated for a subset of data in which samples are excluded if taken later than 2 weeks (14 days) after the previous IMP administration.

SGS	Statistical Analysis Plan	
ARGX-113-2009	Final and Interim Analysis	Final 4.0 of 04NOV2024

Also, the same subgroup analyses will be performed as for efficacy. For the final analysis of Part A data, only the following subgroups are of interest:

[figure not shown]
- Disease history (newly diagnosed versus relapsing)
- Disease severity as per IGA-BP at screening (moderate versus severe)
- BPDAI activity score at baseline: <20, 20-56, >56
- Age at informed consent (18 <65, 65 <75, 75 <85, >=85)

Listings will be created for total IgG, and anti-BP antibodies results over time. Listings will always show the non-imputed results.

4.4 IMMUNOGENICITY

4.4.1 Available data

Blood samples will be collected for the determination of anti-drug antibodies (ADA) to efgartigimod (in serum samples) and antibodies against rHuPH20 (in plasma samples) at the time points indicated in the schedule of assessments (see appendix 9.5).

Immunogenicity samples are analysed in a 3-tiered approach:

- All samples are evaluated in the ADA screening assay and are scored as ADA screening positive or negative.
- If a sample scored positive in the ADA screening assay, it is further evaluated in the confirmatory assay and is scored confirmed positive (positive immunodepletion) or confirmed negative (negative immunodepletion).
- If a sample is scored as confirmed positive, the samples are further characterized in the ADA titration assay (to determine titer) and are also further analyzed in the Neutralizing antibody (Nab) assay to confirm neutralizing activity (positive or negative). For NAb against efgartigimod, a screening assay is performed and results will be reported as negative or positive. For NAb against rHuPH20, the same 3-tiered approach is implemented: the screening NAb assay, followed by a NAb confirmatory assay, and a titer NAb assay, according to the above described 3-tiered approach.

If available, a titer result will be reported for the ADA confirmed positive samples. However, a titer result is not always available:

- If the ADA confirmed positive sample could not be run in the titration assay (e.g., due to insufficient sample volume/quality to perform the titer analysis), the result will be described as 'positive immunodepletion' and the sample should be considered as ADA positive.
- If a sample is negative in the titration assay, it will be reported as 'negative titer' but it should be considered ADA positive because it was confirmed positive in the second tier.
- If a sample could not be analyzed or reported as 'positive screen', the ADA sample status is ADA unevaluable.

This is also applicable to rHuPH20 Ab and rHuPH20 NAb results.

An overview of this 3-tiered approach and all possible ADA or rHuPH20 Ab or rHuPH20 NAb sample results that will be reported by the laboratory is given below. From these reported ADA or rHuPH20 Ab or rHuPH20 NAb sample results a final ADA or rHuPH20 Ab or rHuPH20 NAb sample status needs to be derived during the statistical analysis, as presented in the final column ('Final ADA Outcome'):

[figure not shown]
[figure not shown]
[figure not shown]

Figure 1: ADA sample status

a "Positive titer" is reported if it was not possible to retrieve a numerical value.

4.4.2 Derivation rules

4.4.2.1 PARTICIPANT CLASSIFICATION FOR ADA AGAINST EFGARTIGIMOD

Table 5 below gives an overview of how the ADA participant classification will be derived, starting from the participant baseline ADA sample status.

Table 5: Participant classification for ADA against Efgartigimod

Participant	Highest ^c post-baseline sample status				
ADA classification	ADA negative	ADA positive (missing titer ^a)	ADA positive (negative titer ^b or numeric titer value)		ADA not evaluable
Baseline ADA sample status					
ADA negative	ADA negative	Treatment- Induced ADA	Treatment-In	nduced ADA	ADA unevaluable
ADA positive (missing titer ^a)	Treatment- Unaffected ADA	ADA unevaluable	ADA une	evaluable	ADA unevaluable
ADA positive (negative titer ^b or numeric titer value)	Treatment- Unaffected ADA	ADA unevaluable	titer < 4 x baseline titer: Treatment- Unaffected ADA	titer ≥ 4x baseline titer: Treatment- Boosted ADA	ADA unevaluable
ADA not evaluable	ADA unevaluable	ADA unevaluable	ADA une	evaluable	ADA unevaluable

Samples with missing titer have as reported ADA result 'positive immunodepletion' or 'positive titer,'

ADA evaluable participant = participant classified as any of following categories: ADA negative, treatment-unaffected ADA, treatment-induced ADA, treatment-boosted ADA. The first 2 categories are classified as 'ADA negative', the latter 2 as 'ADA positive'.

ADA unevaluable participant = participant classified as ADA unevaluable or with missing baseline ADA sample or without post-baseline ADA samples.

[figure not shown]
Note: Fourfold difference in titer values is considered significant in case a twofold serial dilution is applied (= 2 times the dilution factor) (reference to Shankar et al., 2014).

ADA incidence = percentage of participants with treatment-induced or treatment-boosted ADAs (denominator: number of evaluable participants).

ADA prevalence = percentage of participants with treatment-unaffected ADA, treatment-induced ADA, or treatment-boosted ADA (denominator: number of evaluable participants).

Results reported as 'negative titer,' i.e., titer value <1 will be set to value of 1;

Elighest sample status, with order: (from low to high): ADA unevaluable, ADA negative, ADA positive (missing titer /positive immunodepletion), ADA positive with titer <= 1 ('negative titer' as reported ADA result, titer value set to 1), ADA positive with titer >1 (i.e., numeric titer and selecting the sample with highest titer)

4.4.2.2 PARTICIPANT CLASSIFICATION FOR ANTIBODIES AGAINST RHUPH20

Table 6 below gives an overview of how the anti-rHuPH20 antibody (rHuPH20 Ab) participant classification will be derived, starting from the participant baseline rHuPH20 Ab sample status.

Table 6: Participant classification for antibodies against rHuPH20

Participant	Highest ^c post-baseline sample status				
anti-rHuPH20 Ab classification	rHuPH20 Ab negative	rHuPH20 Ab positive (missing titer ^a)	rHuPH20 Ab positive (negative titer ^b or numeric titer value)		rHuPH20 Ab not evaluable
Baseline rHuPH20 Ab sample status					
rHuPH20 Ab negative	rHuPH20 Ab negative	Treatment- Induced rHuPH20 Ab	Treatmen rHuPH		rHuPH20 Ab unevaluable
rHuPH20 Ab positive (missing titer ^a)	Treatment- Unaffected rHuPH20 Ab	rHuPH20 Ab unevaluable	rHuPH20 Ab	unevaluable	rHuPH20 Ab unevaluable
rHuPH20 Ab positive (negative titer ^b or numeric titer value)	Treatment- Unaffected rHuPH20 Ab	rHuPH20 Ab unevaluable	titer < 4 x baseline titer: Treatment- Unaffected rHuPH20 Ab	titer ≥ 4x baseline titer: Treatment- Boosted rHuPH20 Ab	rHuPH20 Ab unevaluable
rHuPH20 Ab not evaluable	rHuPH20 Ab unevaluable	rHuPH20 Ab unevaluable	rHuPH20 Ab	unevaluable	rHuPH20 Ab unevaluable

^a Samples with missing titer have as reported rHuPH20 Ab result 'positive immunodepletion' or 'positive titer';

rHuPH20 Ab evaluable participant = participant classified as any of following categories: rHuPH20 Ab negative, treatment-unaffected rHuPH20 Ab, treatment-induced rHuPH20 Ab, treatment-boosted rHuPH20 Ab. The first 2 categories are classified as 'rHuPH20 Ab negative', the latter 2 as 'rHuPH20 Ab positive'.

rHuPH20 Ab unevaluable participant = participant classified as rHuPH20 Ab unevaluable or with missing baseline rHuPH20 Ab sample or without post-baseline rHuPH20 Ab samples

Note: A 4-fold difference in titer values is considered significant in case a twofold serial dilution is applied (reference to Shankar et al., 2014).

Anti-rHuPH20 Ab incidence = percentage of participants with treatment-induced or treatment-boosted rHuPH20 Ab s (denominator: number of evaluable participants).

b Results reported as 'negative titer,' i.e., titer value <5 will be set to value of 5;

^c Highest sample status, with order. (from low to high): rHuPH20 Ab unevaluable, rHuPH20 Ab negative, rHuPH20 Ab positive (missing titer/positive immunodepletion), rHuPH20 Ab positive with titer <= 5 ('negative titer' as reported rHuPH20 Ab result, titer value set to 5), rHuPH20 Ab positive with titer >> 5 (i.e. numeric titer and selecting the sample with highest titer)

SGS	Statistical Analysis Plan		
ARGX-113-2009	Final and Interim Analysis	Final 4.0 of 04NOV2024	

Anti-rHuPH20 Ab prevalence = percentage of participants with treatment-unaffected rHuPH20 Ab, treatment-induced rHuPH20 Ab or treatment-boosted rHuPH20 Ab (denominator: number of evaluable participants).

4.4.2.3 PARTICIPANT CLASSIFICATION FOR NAB AGAINST EFGARTIGIMOD

All ADA confirmed positive samples will also be evaluated in the NAb assay. All samples that were not analyzed in the NAb assay (i.e., the ADA negatives) are per default NAb negative. Also, if a NAb sample is not reported, the NAb sample status is NAb unevaluable.

For NAb against efgartigimod, all samples evaluated in the NAb assay will be scored as NAb positive, NAb negative or NAb unevaluable by the laboratory. Based on these results, the participants will be categorized based on their baseline and post-baseline sample status as detailed in table 7.

Table 7: Participant classification for NAb against Efgartigimod

Participant NAb classification	Highest ^a post-baseline NAb sample status				
	NAb negative	NAb positive	NAb not evaluable		
Baseline NAb sample status					
NAb negative			NAb unevaluable		
NAh positivo	baseline neg – post- baseline neg	baseline neg – post- baseline pos	NAb unevaluable		
NAb positive	baseline pos – post- baseline neg	baseline pos – post- baseline pos	NAO unevaluable		
NAb not evaluable	NAb unevaluable	NAb unevaluable	NAb unevaluable		

^a Highest sample status in order: (from low to high): NAb unevaluable, NAb negative, NAb positive

[figure not shown]
NAb unevaluable participant = participant classified as NAb unevaluable or with missing baseline NAb sample or without post-baseline NAb samples.

NAb incidence = percentage of participants with participant classification 'baseline neg – post-baseline pos' and 'baseline pos – post-baseline pos' (denominator: number of evaluable participants).

NAb prevalence = percentage of participants with participant classification 'baseline neg – post-baseline pos', 'baseline pos – post-baseline pos' or 'baseline pos – post-baseline neg' (denominator: number of evaluable participants).

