Ediphest sample status, with order: (from low to high): rHuPH20 NAb unevaluable, rHuPH20 NAb negative, rHuPH20 NAb positive (missing titer/positive immunodepletion), rHuPH20 NAb positive with titer <100 ('negative titer' as reported NAb result, titer value set to 100), rHuPH20 NAb positive with titer ≥100 (i.e. numeric titer value and selecting the sample with highest titer).

NAb incidence = percentage of participants with participant classification 'treatment-induced rHuPH20 NAb' or treatment-boosted rHuPH20 NAb' (denominator: number of evaluable participants).

NAb prevalence = percentage of participants with participant classification 'treatment-unaffected rHuPH20 NAb', 'treatment-induced rHuPH20 NAb' or 'treatment-boosted rHuPH20 NAb' (denominator: number of evaluable participants).

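### Efgartigimod NAb incidence counts participants who were already NAb positive before the first dose, even with no evidence of boosting

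*SAP*

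**What the plan says.** For NAb against efgartigimod, SAP 4.4.2.3 gives "NAb incidence = percentage of participants with participant classification 'baseline neg – post-baseline pos' and 'baseline pos – post-baseline pos", over evaluable participants. Prevalence in the same section starts from the same two groups, "NAb prevalence = percentage of participants with participant classification 'baseline neg – post-baseline pos', 'baseline pos – post-baseline pos", and adds only those who go from positive to negative.

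The SAP's other three definitions follow a different rule:

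- ADA against efgartigimod (4.4.2.1): "ADA incidence = percentage of participants with treatment-induced or treatment-boosted ADAs".
- Antibodies against rHuPH20 (4.4.2.2): "Anti-rHuPH20 Ab incidence = percentage of participants with treatment-induced or treatment-boosted rHuPH20 Ab s".
- NAb against rHuPH20 (4.4.2.4): "NAb incidence = percentage of participants with participant classification 'treatment-induced rHuPH20 NAb' or treatment-boosted rHuPH20 NAb".

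In each of these three, a baseline-positive participant whose titer does not rise at least 4-fold is treatment-unaffected and enters prevalence only. For ADA, Table 5 of the SAP reads "titer < 4 x baseline titer: Treatment- Unaffected ADA", and the text then groups that class with the negatives: "The first 2 categories are classified as 'ADA negative', the latter 2 as 'ADA positive".

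Only samples confirmed ADA positive go into the efgartigimod NAb assay, and ADA-negative samples are set to NAb negative (4.4.2.3). That assay reports positive or negative without a titer, whereas the rHuPH20 NAb assay has a titer step (4.4.1).

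**The concern.** Incidence normally means antibodies that appear or strengthen on treatment, and the SAP uses the word that way three times out of four. In 4.4.2.3 it means any NAb positivity after baseline. A participant with stable, pre-existing ADA and NAb is then treatment-unaffected in the ADA table and incident in the NAb table. This applies to placebo as well as efgartigimod participants, because both outputs are by treatment on the safety set (SAP 8.1, Tables 14.2.4.1.2 and 14.2.4.1.4).

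What is at stake is how one summary line in the immunogenicity report is read. Protocol 9.3.3.2 names ADA and NAb incidence side by side, so a reader will assume that the word has one meaning.

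**Working it through.** The plan states no figure for this quantity, so there is none to reproduce. The check enumerates the combinations of baseline and post-baseline status that SAP Tables 5 and 7 allow, and then scales the difference.

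**Step 1. Participants who are NAb positive after baseline.**

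| Baseline ADA / NAb | Post-baseline ADA / NAb | ADA class | ADA-incident | NAb-incident as written | NAb-incident if aligned |
|---|---|---|---|---|---|
| neg / neg | pos / pos | induced | yes | yes | yes |
| pos / neg | pos, titer ≥4x / pos | boosted | yes | yes | yes |
| pos / pos | pos, titer ≥4x / pos | boosted | yes | yes | yes |
| pos / neg | pos, titer <4x / pos | unaffected | no | yes | yes |
| pos / pos | pos, titer <4x / pos | unaffected | no | **yes** | **no** |
| pos / neg | pos, a titer missing at either time / pos | unevaluable | not classed | yes | yes |
| pos / pos | pos, a titer missing at either time / pos | unevaluable | not classed | yes | needs a rule |

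The fifth row is the defect. The last row matters for the fix.

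**Step 2. Formulas.** Let N be the number evaluable, a the neg-to-pos count, b the pos-to-pos count with boosted ADA, c the pos-to-pos count without it, and d the pos-to-neg count.

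- Incidence as written = (a + b + c)/N
- Prevalence = (a + b + c + d)/N
- Incidence aligned with the other three definitions = (a + b)/N
- Excess = c/N

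**Step 3. Size per participant.** SAP 1.3 gives about 120 in Part B and about 40 in Part A, each randomized 1:1, so at most about 60 and 20 evaluable per arm.

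- Part B: 1/60 = 1.7 percentage points for each unit of c
- Part A: 1/20 = 5.0 percentage points for each unit of c

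**Step 4. Range over c.** The documents give no baseline NAb rate, so c is an assumption. Take N = 60, three participants with treatment-induced ADA of whom one is NAb positive (a = 1), and b = 0. ADA incidence is 3/60 = 5.0% throughout.

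| c | NAb incidence as written | Aligned |
|---|---|---|
| 0 | 1/60 = 1.7% | 1.7% |
| 1 | 2/60 = 3.3% | 1.7% |
| 3 | 4/60 = 6.7% | 1.7% |
| 5 | 6/60 = 10.0% | 1.7% |

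With no induced or boosted ADA at all and c = 1, ADA incidence is 0/60 = 0%, while NAb incidence as written is 1/60 = 1.7% (1/20 = 5.0% in Part A). The aligned figure is 0%.

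**The case against.** The best defence is the assay. Efgartigimod NAb has no titer, so boosted and unaffected cannot be separated from NAb results, and the rHuPH20 wording cannot simply be copied across. SAP 4.4.3 uses the same two groups as its NAb-positive categories when it sets the threshold of five participants for the correlation tables, which suggests a deliberate choice. This stands as an explanation of the grouping. It does not justify the label, because every pos-to-pos participant has ADA-positive samples at both times and the ADA class already carries the boosting information.

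A second defence is that nothing is hidden. SAP 4.4.3 tabulates the full NAb classification by treatment, and also NAb-positive participants within each ADA class, including the treatment-unaffected class. A careful reader could rebuild the figure. That is true, and it limits the harm to the summary line.

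A reader might infer three stronger points that the documents do not support:

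- *NAb incidence must be a subset of ADA incidence.* The SAP links the two only at sample level. The fourth row of the Step 1 table shows a participant who newly turns NAb positive while the ADA titer stays below 4x: NAb-incident under any sensible rule, but not ADA-incident. Missing ADA titers also make the two denominators differ.
- *Only neg-to-pos is true incidence.* That would drop baseline-positive participants with boosted ADA, whom the ADA rule counts as incident.
- *A named secondary endpoint is misdefined.* Protocol Tables 3 and 4 name ADA against efgartigimod and antibodies against rHuPH20. NAb incidence appears only among the descriptive outputs in Protocol 9.3.3.2.

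**Conclusion.** The definition is wrong as written, in a minor output. It labels as incident those participants who were NAb positive before the first dose and show no boosting, contrary to the SAP's own usage elsewhere, and it gives no reason. The overstatement is c/N: about 1.7 points per such participant in a Part B arm and 5 points in a Part A arm, assuming that nearly all randomized participants are evaluable. Fewer evaluable participants would make each one count for more. The total depends on baseline NAb positivity, which the documents do not give. If nobody is positive at baseline, or if every pos-to-pos participant has boosted ADA, the two definitions give the same number. No primary or key secondary result is touched.

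**What to change.** Choose one of two options in SAP 4.4.2.3 before database lock:

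1. Define NAb incidence as neg-to-pos, plus pos-to-pos only where the participant's ADA class is treatment-boosted. Count the remaining pos-to-pos participants in prevalence only.
2. Keep the present grouping but call it *post-baseline NAb positivity*, and do not present it as incidence.

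Under option 1, state how to treat pos-to-pos participants whose ADA class is unevaluable because a titer is missing. For example, leave them in the denominator, do not count them as incident, and give their number in a footnote. Under either option, check that the five-participant threshold in SAP 4.4.3 still reads as intended; it can keep both groups if it is described as post-baseline positivity.

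The cost is one line of SAP text and a merge of the NAb and ADA classifications, both of which are already derived. No new data or tables are needed.

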4.4.2.4 PARTICIPANT CLASSIFICATION FOR NAB AGAINST RHUPH20

All rHuPH20 Ab confirmed positive samples will also be evaluated in the NAb assay against rHuPH20. All samples that were not analyzed in the NAb assay (i.e., the rHuPH20 Ab negatives) are per default NAb negative. Also, if a NAb sample is not reported, the NAb sample status is NAb unevaluable. Based on these results, the

participants will be categorized based on their baseline and post-baseline sample status as detailed in following table 8.

Table 8: Participant classification for NAb against rHuPH20

Participant	Highest ^e post baseline sample status					
rHuPH20 NAb classification	rHuPH20 NAb negative	rHuPH20 NAb positive (missing titer ^a)	rHuPH20 NAb positive (negative titer ^b or numeric titer value)		rHuPH20 NAb not evaluable	
Baseline rHuPH20 NAb sample status				ž		
rHuPH20 NAb negative	rHuPH20 NAb negative	Treatment Induced rHuPH20 NAb	Treatment Induced rHuPH20 NAb		rHuPH20 NAb unevaluable	
rHuPH20 NAb positive (missing titer ^a)	Treatment Unaffected rHuPH20 NAb	rHuPH20 NAb unevaluable	rHuPH20 NAb unevaluable		rHuPH20 NAb unevaluable	
rHuPH20 NAb positive (negative titer ^b or numeric titer value)	Treatment Unaffected rHuPH20 NAb	rHuPH20 NAb unevaluable	titer < 4 x baseline titer: Treatment Unaffected rHuPH20 NAb	titer ≥ 4x baseline titer: Treatment Boosted rHuPH20 NAb	rHuPH20 NAb unevaluable	
rHuPH20 NAb not evaluable	rHuPH20 NAb unevaluable	rHuPH20 NAb unevaluable	rHuPH20 NAb unevaluable		rHuPH20 NAb unevaluable	

[figure not shown]
Samples with missing titer have as reported rHuPH20 NAb result 'positive immunodepletion' or 'positive titer';

rHuPH20 NAb evaluable participant = participant classified as any of following categories: rHuPH20 NAb negative, treatment-unaffected rHuPH20 NAb, treatment-induced rHuPH20 NAb, treatment-boosted rHuPH20 NAb. The first 2 categories are classified as 'rHuPH20 NAb negative', the latter 2 as 'rHuPH20 NAb positive'.

rHuPH20 NAb unevaluable participant = participant classified as rHuPH20 NAb unevaluable or with missing baseline rHuPH20 NAb sample or without post-baseline rHuPH20 NAb samples

Results reported as 'negative titer,' i.e., titer value <100 will be set to value of 100;

Ediphest sample status, with order: (from low to high): rHuPH20 NAb unevaluable, rHuPH20 NAb negative, rHuPH20 NAb positive (missing titer/positive immunodepletion), rHuPH20 NAb positive with titer <100 ('negative titer' as reported NAb result, titer value set to 100), rHuPH20 NAb positive with titer ≥100 (i.e. numeric titer value and selecting the sample with highest titer).

NAb incidence = percentage of participants with participant classification 'treatment-induced rHuPH20 NAb' or treatment-boosted rHuPH20 NAb' (denominator: number of evaluable participants).

NAb prevalence = percentage of participants with participant classification 'treatment-unaffected rHuPH20 NAb', 'treatment-induced rHuPH20 NAb' or 'treatment-boosted rHuPH20 NAb' (denominator: number of evaluable participants).

